7.5 Post-treatment Phase

7.5.1 End of Treatment Visit

Upon treatment discontinuation, regardless of the reason, patients will have an End of Treatment Visit. For patients that have radiologic disease progression by RECIST v1.1, but continue to derive benefit in the opinion of the investigator, they will be allowed to continue treatment in the Treatment Phase. In such cases, the investigator's decision to continue treatment should be documented in the source documents and the patient must provide additional consent prior to continuing treatment with rucaparib as described starting in [Section 7.4.5](#) and an End of Treatment Visit will occur at the end of all rucaparib treatment. Patients who continue treatment with rucaparib after radiologic disease progression will have the option of tumor tissue biopsy collection at time of first disease progression on study (requires additional consent). Tumor tissue will be processed locally as FFPE tissue. Refer to the Pathology Charter for detailed sample handling instructions.

The following procedures will be performed at the End of Treatment Visit:

- Physical examination
- Weight
- ECOG performance status ([Appendix 2](#))
- Vital signs
- Concomitant medications and any surgical/medical procedures
- 12-lead ECG
- Tumor assessment/ scans if it has been ≥ 8 weeks since the last assessment
- Hematology
- Serum chemistry (fasting is not required)
- Urinalysis
- Serum pregnancy test for women of childbearing potential
- Collect ctDNA blood sample
- AE monitoring
- Patients return all unused tablets and containers (empty, partially used, and/or unopened) to the study site for final accountability.
- Optional tumor tissue biopsy collection after the time of disease progression (radiologic or clinical) and prior to initiation of any subsequent anti-cancer therapy (requires additional consent). Tumor tissue will be processed locally as FFPE tissue. Refer to the Pathology Charter for detailed sample handling instructions.

7.5.2 28-day Follow-up Visit

The following procedures will be performed for all patients at 28 (± 3) days after the last dose of rucaparib.

- Physical examination
- Weight
- ECOG performance status ([Appendix 2](#))
- Vital signs
- Concomitant medications and any surgical/medical procedures
- Tumor assessment only for those patients that have not had radiographic progression confirmed by investigator assessment
- Hematology
- Serum chemistry (fasting is not required)
- Urinalysis

- Collect ctDNA blood sample
- AE monitoring
- Information collected for subsequent treatments and adverse event of special interest (AESI) will require appropriate documentation (ie, laboratory and/ or pathology reports) and should be reported as indicated in [Section 8.9](#).

Patients who do not withdraw from the study at this visit will continue with long-term follow-up as described in [Section 7.5.3](#).

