9.7.1 Adverse Events

Adverse events will be classified using the Medical Dictionary for Regulatory Activities (MedDRA) classification system. The severity of the toxicities will be graded according to the NCI CTCAE Version 4.03 or later. Only treatment-emergent adverse events (TEAEs) will be collected: TEAEs are defined as AEs with onset date on or after the date of first dose of rucaparib until the date of the last rucaparib dose plus 28 days.

The number and percentage of patients who experienced TEAEs for each System Organ Class (SOC) and Preferred Term (PT) will be presented. Multiple instances of the TEAE in each SOC and multiple occurrences of the same PT are counted only once per patient. The number and percentage of patients with at least 1 TEAE will also be summarized.

Separate tables will be presented as follows:

- All TEAEs;
- TEAEs by CTCAE grade;
- Grade 3 or higher TEAEs;
- Treatment-related TEAEs;
- Serious TEAEs;

- TEAEs with an outcome of death;
- TEAEs leading to discontinuation of study medication;
- TEAEs resulting in interruption/delay of study medication; and
- TEAEs resulting in dose reduction of study medication.

The incidence of TEAEs will be summarized by relationship to rucaparib according to the following categories: “treatment-related,” or “not treatment-related.” If a patient experiences multiple occurrences of the same AE with different relationship categories, the patient will be counted once, as a relationship category of treatment-related.

If a patient experiences multiple occurrences of the same AE with different toxicity grades, the patient will be counted once for the maximum (most severe) toxicity grade. AEs with a missing toxicity grade will be presented in the summary table with a toxicity grade of “Missing.” For each toxicity grade, the number and percentage of patients with at least 1 TEAE of the given grade will be summarized.

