9.7.2 Clinical Laboratory Evaluations

Clinical laboratory evaluations include the continuous variables for hematology, serum chemistry, and urinalysis. The laboratory values will generally be presented in International System of Units (SI) units. The on-treatment period will be defined as the time from the first dose of rucaparib to 28 days after the last dose of rucaparib. Laboratory values collected during the on-treatment period will be included in the summary tables. The laboratory values collected after the on-treatment period will only be presented in the data listings.

The summary of laboratory data will include shift tables based on CTCAE for shifts in grade from baseline to maximum, minimum, and last value during the on-treatment period.

Supporting laboratory data including normal ranges and abnormal laboratory flags will be provided using by-patient listings. Separate listings will be produced for clinically significant laboratory abnormalities (ie, those that meet Grade 3 or 4 criteria according to CTCAE).

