9.2.2 Progression-free Survival

Progression-free survival (PFS) is defined as the time from first dose of rucaparib to the date of first objective evidence of progression documented by the investigator per RECIST v1.1 or death due to any cause, whichever occurs first, plus 1 day. Patients without a documented event of progression will be censored on the date of their last adequate post-baseline tumor scan or date of first dose of study drug if no tumor scans have been performed. If a patient discontinues study drug due to something other than PD and subsequently begins another anti-cancer therapy (ACT) prior to a PFS, that patient will be censored at the last tumor scan prior to the start of ACT. However, PFS events occurring more than 90 days after discontinuation of study drug, but prior to start of subsequent ACT, will not be included in

the analysis and such patients will be censored at their last scan prior to the end of the 90-day window.

PFS will be summarized in a Kaplan-Meier plot; however in the case of a low censoring rate, it may be summarized with descriptive statistics.

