11.1 Adverse Events

Adverse events will be classified using the MedDRA classification system. The severity of the toxicities will be graded according to the National Cancer Institute (NCI) Common Terminology Criteria for Adverse Events (CTCAE) whenever possible. Treatment-emergent adverse events (TEAEs) are defined as AEs with onset date on or after the date of first dose of study medication until the date of the last study medication dose plus 28 days. Adverse events will be considered treatment-emergent if all or part of the date of onset of the AE is missing and it cannot be determined if the AE meets the definition for treatment-emergent.

The number and percentage of patients who experienced TEAEs for each system organ class and preferred term will be presented. Multiple instances of the TEAE in each system organ class and multiple occurrences of the same preferred term are counted only once per patient. The number and percentage of patients with at least one TEAE will also be summarized.

The incidence of TEAEs will also be summarized by relationship to study drug according to the following categories: “treatment-related,” or “not treatment-related”. If a patient

experiences multiple occurrences of the same AE with different relationship categories, the patient will be counted once, as a relationship category of treatment-related.

If a patient experiences multiple occurrences of the same AE with different toxicity grades, the patient will be counted once for the maximum (most severe) toxicity grade. AEs with a missing toxicity grade will be presented in the summary table with a toxicity grade of "Missing." For each toxicity grade, the number and percentage of patients with at least one TEAE of the given grade will be summarized.

The time to the first TEAE and first treatment-related TEAE that results in a dose reduction, delay, interruption, or discontinuation of study drug is defined as 1+ the number of days from the first dose of study drug to the start of the first TEAE.

Separate tables will be presented including but not limited to:

- All TEAEs;
- TEAEs by CTCAE grade;
- Grade 3 or greater TEAEs;
- Treatment-related TEAEs, overall and by categories: CTCAE grade, grade 3 or greater, resulting in dose reduction, resulting in dose interruption, resulting in dose discontinuation, outcome of death;
- Serious TEAEs, overall and by categories: age, sex, and treatment-relatedness;
- TEAEs with an outcome of death;

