11.2 Clinical Laboratory Evaluations

Clinical laboratory evaluations include the continuous variables for hematology, serum chemistry, and urinalysis. The laboratory values will generally be presented in International System (SI) units. The on-treatment period will be defined as the time from first dose to 28 days after the last dose of study drug. Laboratory values collected during the on-treatment period will be included in the summary tables. The laboratory values collected after the on-treatment period will only be presented in the data listings.

The summary of laboratory data will include shift tables based on CTCAE for shifts in grade from baseline to maximum, minimum, and last value during the on-treatment period.

The summary of laboratory data will include descriptive statistics (N, mean, StD, minimum, median, and maximum) of the maximum, minimum, and last value during the on-treatment period. Summaries using descriptive statistics of the change from baseline to the maximum, minimum, and last value during the on-treatment period will also be given.

Supporting laboratory data including normal ranges and abnormal laboratory flags will be provided using by-patient listings. Separate listings will be produced for clinically significant laboratory abnormalities (ie, those that meet Grade 3 or 4 criteria according to CTCAE).

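### The TEAE and laboratory/vital-sign windows run to last dose + 28 days without stopping at subsequent anti-cancer therapy, so toxicity of the next drug could be counted in rucaparib's safety tables

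*Protocol*

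**What the plan says.** **Adverse events.** Protocol 9.7.1 counts as treatment-emergent any event from first dose "until the date of the last rucaparib dose plus 28 days". SAP 11.1 uses the same limit: "until the date of the last study medication dose plus 28 days".

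**Laboratory values and vital signs.** Protocol 9.7.2 states: "The on-treatment period will be defined as the time from the first dose of rucaparib to 28 days after the last dose of rucaparib". SAP 11.2 repeats it: "The on-treatment period will be defined as the time from first dose to 28 days after the last dose of study drug". Protocol 9.7.3 and SAP 11.3 apply the same period to vital signs. The laboratory tables then show "shifts in grade from baseline to maximum, minimum, and last value during the on-treatment period". Later values are listed only.

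**Data collection.** Protocol 7.5.2 opens with "The following procedures will be performed for all patients at 28 (± 3) days after the last dose of rucaparib", and its procedures include hematology, chemistry, vital signs and AE monitoring. The same list has an item that begins "Information collected for subsequent treatments".

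**Efficacy, by contrast.** For a patient who stops rucaparib for a reason other than progression and starts another anti-cancer therapy (ACT) before a PFS event, SAP 9.2.2 says "that patient will be censored at the last tumor scan prior to the start of ACT". None of the safety sections has a counterpart to this rule.

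**The concern.** Safety and tolerability is a secondary objective, read from a single arm with no control group against which to judge background toxicity. The summaries are sensitive to one bad value: AE tables take the highest grade per patient, and laboratory tables take the extreme and last values in the window. If a patient has started another drug, one low count after the switch can become the worst grade shown for rucaparib. Protocol 1.3.2.2.3 names anemia and neutropenia among the commonest Grade 3 or higher events on rucaparib, so a next drug that also suppresses the marrow could not be told apart in these tables.

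The plan itself allows for early switching. Protocol 10.1 lists, as a reason to stop rucaparib, clinical progression that calls for an immediate change of systemic therapy, and Protocol 7.5.2 records subsequent treatment at the 28-day visit.

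**Working it through.** The plan states no figure on this point, so there is none to reproduce. The check has three parts.

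**1. Is there a cut anywhere?**

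| Data | Where | End of window | Stops at next therapy? |
|---|---|---|---|
| TEAEs | Protocol 9.7.1, SAP 11.1 | last dose + 28 days | No |
| Laboratory | Protocol 9.7.2, SAP 11.2 | last dose + 28 days | No |
| Vital signs | Protocol 9.7.3, SAP 11.3 | last dose + 28 days | No |
| PFS | SAP 9.2.2 | event or censoring | Yes |
| Off-treatment tumor scans | Protocol 7.5.3 | progression or other stop | Yes |
| Optional biopsy | Protocol 7.5.1 | after progression | Yes, must come before it |

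**2. How much of the safety window lies after the last dose?** The synopsis gives a historical 2 to 3 months to progression for most patients with relapsed disease. Assume time on rucaparib equals that, at 30.4375 days per month.

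- 2 months: 28 / (60.9 + 28) = 31.5%
- 3 months: 28 / (91.3 + 28) = 23.5%

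The post-dose period could thus be roughly a quarter to a third of a typical patient's window.

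**3. What could it do to an incidence?** Let p be the true incidence on rucaparib, f the share of patients who start a new therapy within 28 days of the last dose, and g the chance that the new drug causes the event inside the remaining window. With independence,

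observed incidence = 1 − (1 − p)(1 − f·g), so the rise is (1 − p)·f·g.

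The documents give none of p, f or g; all are assumed. N = 200 is the planned enrollment.

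| p | f | g | Observed | Rise (points) | Extra patients of 200 |
|---|---|---|---|---|---|
| 30% | 0 | any | 30.0% | 0 | 0 |
| 30% | 10% | 10% | 30.7% | 0.7 | 1.4 |
| 30% | 20% | 30% | 34.2% | 4.2 | 8.4 |
| 30% | 40% | 50% | 44.0% | 14.0 | 28.0 |
| 50% | 20% | 30% | 53.0% | 3.0 | 6.0 |

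**Allowance for the visit window.** The visit may fall on days 25 to 31, and draws on days 29, 30 and 31 are outside the on-treatment period. If visits spread evenly over those seven days (an assumption) and the 28-day draw is the only source, 4/7 of draws count. The rises at p = 30% become 0.7 × 4/7 = 0.4, 4.2 × 4/7 = 2.4 and 14.0 × 4/7 = 8.0 points.

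**The case against.** **Protocol 6.3 bars other anti-cancer therapy.** It does so, apart from palliative radiotherapy, for as long as the patient participates in the study, so a switch might seem impossible. The synopsis limits the bar to the time on rucaparib. The wider reading also does not fit Protocol 3.1.3, 7.5.2 and 7.5.3 or SAP 9.2.2, which all provide for subsequent treatment during follow-up. A bar would in any case not remove the data of a patient who switched. What stands is that the two passages need reconciling.

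**The plan already separates causes.** SAP 11.1 tabulates treatment-related TEAEs by grade, Grade 3 or greater, dose action and death, and splits serious TEAEs by relatedness. Protocol 8.7.4 classes events due to other medications as not related. Clinically significant laboratory abnormalities are also recorded as AEs, each with a causality assessment (Protocol 7.6.4.2, 8.5 and 8.7). This stands as real mitigation for AEs, though it rests on open-label judgement. It leaves the all-cause tables as they are, and the laboratory shift and extreme-value tables use every value whatever its cause.

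**Early switching is not shown to be common.** This stands. A reader might infer a high rate from the 14-day washout at entry, but that rule governs entry to this trial, not what happens after rucaparib. Nor do the documents say that docetaxel, paclitaxel or vinflunine would come next; they describe these as second-line options, call later options limited, and allow rucaparib beyond progression.

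**A cut creates the opposite bias.** This stands too. A fixed 28-day window catches delayed toxicity. Laboratory values carry no causality flag, so a cut drops a continuing rucaparib cytopenia along with the next drug's effect, and Protocol 5.4.1.2 provides for anemia not resolved after 42 days off drug. That argues for showing both versions, not for leaving the rule as it is.

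**Conclusion.** The gap is real: no safety window in either document stops at subsequent therapy, although the plan expects such therapy and cuts PFS at it. Next-drug toxicity could therefore enter the all-cause, Grade 3 or higher, serious and fatal TEAE tables and the laboratory and vital-sign summaries. For incidence and worst grade the effect can only be upward; for last values it may go either way.

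The size is unknown and is zero if nobody switches within 28 days. At an assumed true incidence of 30%, with 10-40% switching and 10-50% of those having a new event, the rise is 0.7 to 14 points; on the day 25-31 assumption it is 0.4 to 8.0 points if the 28-day draw is the only source.

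A reader might infer that the safety tables will be materially contaminated, or that the 28-day window is wrong and should be replaced. The documents support neither: they give no switching rate, and the uncut window has a purpose. The visit schedule in Protocol 7.5.2 is not at fault either; the definitions in Protocol 9.7 and SAP 11 are what need the addition. The primary ORR analysis, the futility rule and the sample size are unaffected.

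**What to change.** 1. In SAP 11.1-11.3 and Protocol 9.7.1-9.7.3, prespecify the all-cause TEAE, laboratory and vital-sign summaries with the window ended at the earlier of last dose + 28 days and the day before the first subsequent anti-cancer therapy.
2. Keep AEs judged related to rucaparib in these summaries through day 28.
3. Present the uncut 28-day tables alongside, and flag post-switch events and values in the listings.
4. Confirm that the start date of subsequent therapy is recorded. Protocol 7.5.2 speaks only of information on subsequent treatments, but the PFS rule in SAP 9.2.2 already needs this date.
5. Reconcile the synopsis and Protocol 6.3 on how long other anti-cancer therapy is barred.

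The cost is SAP and protocol wording, one date comparison and one extra set of tables. In the cut version, a continuing or late rucaparib effect seen only after the switch is not counted unless it is an AE judged related; laboratory values have no such rescue. The uncut tables cover that loss. AE collection and reporting stay as they are.

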7.5.3 Long-term Follow-up

Patients who complete a 28-day Follow-up Visit after the last dose of rucaparib will continue in long-term follow-up as described below.

- If applicable, tumor assessment (using the same methodology as was used at initial study screening [eg, CT scan or MRI scan if required by local authorities]) when the reason for treatment discontinuation was other than death or disease progression based on radiologic assessment and it has been ≥ 8 weeks since last scan or disease progression was noted on the last scan. Tumor assessment should continue to be performed at the end of every 8 calendar weeks (± 7 days) relative to Cycle 1 Day 1 up to 18 months, then every 12 calendar weeks (± 7 days), until confirmed radiologic disease progression by RECIST v1.1 criteria as assessed by the investigator, loss to follow-up, withdrawal, death, initiation of subsequent treatment, or study closure.
- All patients discontinued from treatment, regardless of reason, will be followed and information collected for subsequent treatments and survival every 12 weeks from last dose of rucaparib until death, loss to follow-up, withdrawal of consent from study, or closure of the study. Follow-up can be performed via the telephone and can be completed to coincide with scheduled tumor assessments.
- SAEs related to rucaparib and all AESIs, irrespective of causality, are to be reported as specified in [Section 8.9](#).

7.6 Methods of Data Collection

7.6.1 Medical History and Demographic/ Baseline Characteristics

Basic demographic and baseline characteristics will be collected during screening. In addition to the evaluation of a patient's medical history in terms of study eligibility, all relevant medical conditions will be documented on the appropriate eCRF. Events that occur after signing of informed consent, but prior to initiation of rucaparib, unless serious and due to a protocol-mandated procedure, should be recorded on the Medical History eCRF.

The patient's entire oncology history will be collected on the appropriate eCRF including date of diagnosis for urothelial carcinoma (and other malignancy, if applicable), prior surgeries/treatments received for cancer, dates of treatment administration, best response

achieved, date of progression and how assessed, and BRCA or other HRR gene mutation status (if known).

7.6.2 Prior and Concomitant Medication Assessments

Medications being used by the patient will be recorded as prior medications during screening and as concomitant medications following receipt of the first dose of rucaparib through the completion of the 28-day Follow-up Visit after treatment discontinuation. Medications information will be entered in the appropriate eCRF after it is obtained at each study visit.

7.6.3 Efficacy Evaluations

Target and non-target lesions will be evaluated for evidence of radiographic response based on RECIST v1.1 criteria.

Tumor assessments will be performed during screening (baseline), at the end of every 8 calendar weeks (± 7 days) relative to the first dose of rucaparib (Cycle 1 Day 1) up to 18 months, then every 12 calendar weeks (± 7 days), until confirmed radiologic disease progression by RECIST v1.1 criteria as assessed by the investigator, loss to follow-up, withdrawal from study, death, or study closure. Tumor assessments should be performed at the time of treatment discontinuation if the reason was other than radiologically confirmed disease progression and it has been ≥ 8 weeks since the last assessment. If treatment was discontinued for reasons other than radiologic disease progression or death, radiologic tumor assessment (using the same methodology as was used at initial study screening) will continue until confirmed radiographic disease progression by RECIST v1.1 per investigator, death, loss to follow-up, withdrawal from the study, study closure, or initiation of subsequent treatment.

Tumor assessments should consist of clinical examination and appropriate imaging techniques (ie, CT scans of the chest, abdomen, and pelvis with appropriate slice thickness per RECIST v1.1); other studies (magnetic resonance imaging (MRI), X-ray, positron emission tomography [PET]/CT, and ultrasound) may also be performed if required. MRI may be used in place of CT scans for assessment of target lesions if required by local authorities. If a site can document that the CT performed as part of a PET/CT is of identical diagnostic quality to a diagnostic CT (with IV and oral contrast) then the CT portion of the PET/CT can be used for RECIST measurements. All sites of disease should be followed and the same methods used to detect lesions at baseline are to be used to follow the same lesions throughout the clinical study. If a patient has known brain metastases, this disease should be evaluated at each required assessment time.

If a complete response (CR) or partial response (PR) is noted, confirmatory scans should be performed at least 4 weeks after response was first documented.

Copies of CT scans (and other imaging, as appropriate) will be collected from all patients. IRR may be conducted on all or a subset of CT scans.

